### 2 Study Objectives

#### 2.1 Primary Objectives

- To evaluate the safety and tolerability of single or repeat intramuscular (IM) administration of G03-52-01 in healthy adult subjects
- For Cohorts 1-3 (Cohorts 1-2 active IP and Cohort 3 is placebo)
  - Demonstrate target protective concentration (NAC) value  $> 0.02$  U/mL (BoNT/A) or  $> 0.03$  U/mL (BoNT/B) at Day 45 and Day 90
  - To evaluate lot-to-lot variability of two doses of G03-52-01 (Note: There will be no formal statistical analysis to support evaluation of lot-to-lot variability. In table summaries, the two lots within each of Cohorts 1 and 2 will be summarized and displayed separately to visually assess lot-to-lot variability.)
- For Cohort 4 (only active IP), demonstrate target protective concentration (NAC) value of BoNT/A and BoNT/B at 4 and 8 hours post-dose

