### 9.10 Analysis of Study Endpoints

#### 9.10.1 Primary Endpoint 1a – Adverse Events, Cohorts 1-4

In order to evaluate primary objective #1, to evaluate the safety and tolerability of repeat intramuscular (IM) administration of G03-52-01 in healthy adult subjects, primary endpoint #1a will be used:

The occurrence of adverse events (AEs) and serious adverse events (SAEs) following administration of G03-52-01 to the final visit

Adverse events (AEs) will be captured in a log at all scheduled visits from Baseline/Dosing [Visit 2 (Day 1)] through the end of study. Unless specified otherwise, AEs summaries will include all events starting from the date of initial administration of G03-52-01 up to and including the date of each subject’s final scheduled

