## Statistical Analysis Plan (SAP)

---

study visit. AEs with a start date after subjects' final scheduled study visit will not be included in table summaries. All AEs captured in the database will be included in subject listings.

All AEs with the exception of reactogenicity events will be classified by Primary System Organ Class (SOC) and Preferred Term (PT) according to the Medical Dictionary for Regulatory Activities (MedDRA®) version 25.0. All AEs that occur after the initiation of study medication will be included in TFL summaries. Table summaries will include the frequency and percentage of subjects experiencing each event, as well as the total number of events experienced at each level of summarization (i.e., SOC and PT within SOC). The following summaries will be presented for all AEs, medically attended adverse events (MAAEs), and serious adverse events (SAEs) by SOC and PT and by treatment group and for all subjects:

- Overall (i.e., regardless of severity or relationship to treatment)
- By maximum severity grade (mild, moderate, or severe)
- By closest relationship to study medication

Additionally, an overall summary irrespective of SOC/PT categorization will be presented separately for all AEs with the exception of reactogenicity events. This overall summary will tabulate the number of subjects and events for: AEs, MAAEs, Grade 3 or greater AEs, AEs related to IP (possibly related or definitely related), Grade 3 or greater AEs related to IP (possibly related or definitely related), AEs with outcome of death, SAEs, SAEs related to IP (possibly related or definitely related), AEs leading to study discontinuation, AEs leading to discontinuation of IP, and AEs related to IP that led to discontinuation of IP.

Furthermore, a separate table will summarize the frequency and percentage of subjects experiencing each reactogenicity event and the total number of events experienced per term. The summary will be broken down by dose (i.e., Dose 1 and Dose 2) for Cohorts 1-3. Events that occur on or after date of first dose and before date of second dose will be summarized under Dose 1. Events that occur on or after date of second dose will be summarized under Dose 2. Reactogenicity events will be broken down into local reactions (injection site pain, injection site tenderness, injection site redness, injection site swelling) and systemic reactions (fever, headache, myalgia, abdominal pain, anorexia, nausea, vomiting, diarrhea, and malaise/fatigue).

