Finally, three AE tables will be produced combining data across all four cohorts with the goal of comparing AE rates following initial administration of IP and before subjects in the first three cohorts received their second dose. For Cohorts 1-3, all AEs will be included that occur starting from the date of initial administration of G03-52-01 and prior to the date of each subjects' second dose. For Cohort 4, all AEs will be included that occur starting from the date of initial administration of G03-52-01 and prior to the date each subject's Day 45 study visit. If a Cohort 4 subject does not attend their Day 45 study visit, then all AEs will be included that occur up to and including 44 days from the subject's initial administration of G03-52-01. For these three AE summaries, Cohort 1 and Cohort 2 subject groupings will include both DP lots and the two Placebo groups (Cohorts 3 and 4) will be pooled together, such that the treatment groupings are as follows: Cohort 1, 50 mg (Both Lots); Cohort 2, 100 mg (Both Lots); Cohort 4, 100 mg; Cohorts 3 and 4, Placebo; and

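### No planned table compares unsolicited adverse events after the second dose with re-dosed placebo in Cohorts 1-3

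*SAP*

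**What the plan says.** **Objective.** SAP 2.1 words it as "To evaluate the safety and tolerability of single or repeat intramuscular (IM) administration of G03-52-01 in healthy adult subjects", and Protocol 4.1 also covers both single and repeat dosing. SAP Table 2, 9.10.1 and 9.10.2 name repeat dosing alone; in 9.10.1 endpoint 1a is there "to evaluate the safety and tolerability of repeat intramuscular (IM) administration of G03-52-01 in healthy adult subjects".

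**AE windows in SAP 9.10.1.**
- The default window runs from first dose to the last planned visit: "AEs summaries will include all events starting from the date of initial administration of G03-52-01 up to and including the date of each" (the sentence then names that visit). AEs, medically attended AEs and serious AEs are tabulated this way overall, by severity and by relationship.
- Three further tables are planned "with the goal of comparing AE rates following initial administration of IP and before subjects in the first three cohorts received their second dose". They stop just before Dose 2 in Cohorts 1-3 and just before the Day 45 visit in Cohort 4. In these tables lots are pooled and "the two Placebo groups (Cohorts 3 and 4) will be pooled together".
- Reactogenicity, meaning a fixed list of local and systemic reactions: "The summary will be broken down by dose (i.e., Dose 1 and Dose 2) for Cohorts 1-3". The rule is that "Events that occur on or after date of second dose will be summarized under Dose 2".

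**Counting and denominator.** A subject counts once at each level of summary (SAP 9.10.1). The denominator is the Safety population, that is, anyone with at least one dose (SAP 7.1.2).

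**Protocol.** Section 11.5.3 summarises all AEs after the start of study medication and has no split by dose.

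**The concern.** Cohort 3 is randomised concurrently with Cohorts 1 and 2 and receives placebo again on Day 45. The trial can therefore ask directly whether a second exposure raises the rate of unsolicited events. The protocol gives grounds for asking: section 3.3.1 lists hypersensitivity-type reactions and anti-drug antibody formation as risks, and section 3.2 counts repeat dosing among the product's expected advantages.

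The SAP splits pharmacodynamic parameters and reactogenicity by dose, and pharmacokinetic parameters by dose where applicable. Unsolicited AEs, which belong to a primary endpoint, get a table for the first-dose period and none for the second. An excess after Dose 2 would be seen only after mixing with events before Dose 2 and with later background events up to Day 240.

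**Working it through.** The plan states no AE rate, effect size or power for AEs, so there is no figure to reproduce.

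**1. Which windows exist (Cohorts 1-3)**

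| Event type | Day 1 to final visit | Before Dose 2 | From Dose 2 |
|---|---|---|---|
| Unsolicited AEs | yes | yes | none |
| Medically attended and serious AEs, by system organ class and preferred term | yes | none separately | none |
| Solicited reactogenicity | not applicable | yes | yes |

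By nominal days, time before Dose 2 is 45 − 1 = 44 of 239 days (18%). Time after it is 240 − 45 = 195 of 239 days (82%).

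**2. Can the missing comparison be derived?**

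- *Subjects.* Let W be the number with an AE over the whole study and P the number with one before Dose 2. Subjects with AEs in both periods are counted once in W. The number with an AE after Dose 2 is therefore only bounded, between W − P and W.
- *Events.* For Cohorts 1 and 2, whole-study events minus pre-Dose-2 events gives post-Dose-2 events, provided both tables cover the same event types. For placebo this fails. The pre-Dose-2 column pools Cohort 3 (75) with Cohort 4 placebo (50), 125 subjects in all, so there is no Cohort 3 figure to subtract.
- *Denominator.* Subjects who received only one dose stay in the whole-study denominator.

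**3. Size of the dilution (assumed rates)**

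Assume a constant background risk b of any event in the category per 45 days, and a risk h in the active arm during the 45 days after Dose 2 only. Take follow-up as 240/45 = 5.33 such intervals.

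- Placebo, whole study: 1 − (1 − b)^5.33
- Active, whole study: 1 − (1 − b)^4.33 × (1 − h)
- Difference: (h − b) × (1 − b)^4.33

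| b | h | Placebo | Active | Difference shown | True excess in window |
|---|---|---|---|---|---|
| 10% | 20% | 43.0% | 49.3% | 6.3 points | 10 |
| 20% | 30% | 69.6% | 73.4% | 3.8 points | 10 |
| 30% | 40% | 85.1% | 87.2% | 2.1 points | 10 |

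For rare categories the share kept, (1 − b)^4.33, is 92% at b = 2%, 96% at 1% and 98% at 0.5%. At b = 0.5%, a 5-point excess appears as 2.6% against 7.5%, or 4.9 points. The first-45-day tables show none of the excess at any b.

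**4. Does the length of the new window matter?**

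Let e be an independent extra risk soon after Dose 2. The difference shown is then e × (1 − background risk in the window). Take e = 10% and a whole-study background of 50% at a constant hazard:

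- Whole study: 10 × (1 − 0.500) = 5.0 points
- Open-ended from Dose 2: 10 × (1 − 0.432) = 5.7 points
- 45 days from Dose 2: background 1 − 0.5^(45/239) = 12.2%, so 10 × (1 − 0.122) = 8.8 points
- 28 days from Dose 2: 10 × (1 − 0.078) = 9.2 points

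An open-ended post-Dose-2 table gains little, because 82% of follow-up already lies there. The gain comes from a bounded window.

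**The case against.** The other side has real points.

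- **The objective is wider than repeat dosing.** A reader of SAP 9.10.1 alone might infer that repeat dosing is the whole primary safety objective. SAP 2.1 and Protocol 4.1 do not support that, and Cohorts 1-3 also serve Day 45 neutralising concentration, sampled before Dose 2, and lot-to-lot variability. Repeat dosing is nonetheless part of the objective, and it is the only regimen in these cohorts.
- **The second dose is not ignored.** A reader might infer that nothing planned looks at it. In fact solicited reactions are tabulated for Dose 2, laboratory values and vital signs are summarised at visits after it, and hypersensitivity-panel results are listed. The whole-study AE tables compare the two-dose regimen with re-dosed placebo, and every AE is listed. The gap is confined to tables of unsolicited AEs, medically attended AEs and serious AEs.
- **Delayed hypersensitivity would not be hidden by dilution.** It would be sought at preferred-term level, where background is low and step 3 shows over 90% of an excess surviving at a background of 2% or less. The dilution argument applies to common categories.
- **Some subtraction is possible.** Active-arm event totals can be obtained if event scopes match. Subject counts and the Cohort 3 placebo figure cannot.
- **The trial is descriptive** (SAP 6), and no estimate now in the plan is wrong. This stands, and it limits the weight of the point.

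Table shells are in a separate document and were not seen. The SAP text does not call for such a table.

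**Conclusion.** The point holds as a gap in the planned displays, not as an error in an existing one. SAP 9.10.1 has no table of unsolicited events starting on or after Dose 2 against re-dosed placebo, and the placebo half of that comparison cannot be rebuilt from the planned tables.

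The cost in visibility depends on the category. Under the assumed constant backgrounds, between about a third and four fifths of a 10-point excess is lost for common categories, and less than a tenth for rare ones. Those sizes rest on invented rates and on an excess confined to the 45 days after Dose 2; only the direction follows from the plan itself. The change is a cheap improvement that lets the trial address re-exposure directly.

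**What to change.** In SAP 9.10.1, for Cohorts 1-3:

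1. Add the same three AE summaries (overall; by system organ class, preferred term and maximum severity; by system organ class, preferred term and closest relationship) for AEs starting on or after the Dose 2 date and before the Day 90 visit, or within 44 days after Dose 2 if that visit is missed. Denominator: subjects who received Dose 2. Columns: Cohort 1, Cohort 2 and Cohort 3 placebo only.
2. Add a Cohort-3-only placebo column to the existing first-45-day tables, so that both doses have the same comparator over windows of similar length.
3. Report by arm the number not given Dose 2, with reasons.

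**Cost.** Three tables and one column, using dates already collected and rules already written. Protocol 3.1.3 says Cohorts 1-3 have completed their visits, so no new data are needed; if unblinded results have been seen, label the tables as added afterwards.

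**Downsides.** There will be more small-count descriptive tables. The Dose 2 denominator is also selected after randomisation: subjects stopped after a Dose 1 event drop out of it, possibly unequally by arm. The new tables should therefore supplement the whole-study tables and not replace them.

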The safety and pharmacokinetics (PK) of G03-52-01 were evaluated in a Phase 1 clinical study of a single IM injection of G03-52-01 conducted by Resilience Government Services (RGS). There were no safety concerns with the administration of the DP. All subjects in Cohorts 1-3 of the Phase 2 clinical study completed their last subject visit. All available safety data was reviewed by the DSMB and no safety concerns were identified.

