## Statistical Analysis Plan (SAP)

**Table 1: Details of Study Cohorts**

Study Cohort	Expected Number of Subjects	Dosing Day(s)	Drug Product Lot	Group
Cohort 1 50 mg G03-52-01	150	1, 45	Lot 1 (n=75)	Group 1 50 mg Lot 1
			Lot 2 (n=75)	Group 2 50 mg Lot 2
Cohort 2 100 mg G03-52-01	150	1, 45	Lot 1 (n=75)	Group 3 100 mg Lot 1
			Lot 2 (n=75)	Group 4 100 mg Lot 2
Cohort 3 Placebo	75	1, 45	NA	Group 5 Placebo
Cohort 4 100 mg G03-52-01	200	1	NA	Group 6 100 mg
Cohort 4 Placebo	50	1	NA	Group 7 Placebo
Total	625			

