### 3.3 Randomization and Blinding

For Cohorts 1-3, eligible subjects will be randomized to one of the 5 parallel treatment groups (50 mg G03-52-01 Lots 1 and 2, 100mg G03-52-01 Lots 1 and 2, and Placebo) in a 1:1:1:1:1 ratio, respectively, via the centralized randomization using Interactive Response Technology (IRT) randomization system (Table 1). Cohort 1-3 subjects will receive one dose of either G03-52-01 or Placebo on Days 1 and 45 for a total of two doses. No stratification will be performed for randomization.

For Cohort 4, eligible subjects will be randomized into one of 2 treatment groups (100 mg G03-52-01 or Placebo) in a 4:1 ratio. Cohort 4 subjects will receive one dose of either G03-52-01 or Placebo on Day 1. No stratification will be performed for randomization.

The ICON Randomization Development Team will generate the randomization schedule according to the sponsor protocol number G03-52-01-002, V4.0, 14Apr2024. The ICON team will deliver dummy and live randomization schedules to the IVRS System Development Team via a password-protected .zip file sent through e-mail.

The study staff participating in the administration of study product and assessment of the subjects and the subjects will be refrained from understanding the contents of the IM vial and are blinded from the study product information. Please refer to the Cohorts 1-3 Randomization Plan, v1.0, 16May2022 and Cohort 4 Randomization Plan, v1.0, 18Apr2024 for the detailed randomization list preparation and implementation.

The Investigator may unblind a subject's treatment assignment only in the case of an emergency or a serious adverse event (SAE) when knowledge of the study treatment is essential to the appropriate clinical management or welfare of the subject. Whenever possible, the Investigator should first discuss the options

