## Statistical Analysis Plan (SAP)

---

Total. The number of AEs and the number and percentage of subjects that experienced the given AE will be summarized by the above mentioned treatment groupings.

The three AE summaries will consist of:

- Overall Summary of Adverse Events within First 45 Days of Initial Administration of IP
- Adverse Events within First 45 Days of Initial Administration of IP by System Organ Class, Preferred Term, and Maximum Severity
- Adverse Events within First 45 Days of Initial Administration of IP by System Organ Class, Preferred Term, and Closest Relationship to Study Medication

Unless otherwise specified, at each level of subject summarization of AEs, a subject will be counted once, even if they reported more than one event. If more than one occurrence of an event is reported, the event of the worst severity or the worst-case relationship assessment will be summarized. In summaries by SOC and PT, adverse events will be sorted in descending frequency by SOC and PTs within each SOC according to the total number of events among all subjects.

All AE summaries will be presented for the Safety population.

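### The three first-45-days adverse-event tables pool two non-concurrent placebo groups and set no cut-off for Cohorts 1-3 subjects who never receive Dose 2

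*SAP*

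**What the plan says.** SAP Section 9.10.1 ends with three adverse-event tables across all four cohorts, produced "with the goal of comparing AE rates following initial administration of IP" and before Cohorts 1-3 receive Dose 2. One is an overall summary. The other two are by system organ class and preferred term, one by maximum severity and one by closest relationship. The first is titled "Overall Summary of Adverse Events within First 45 Days of Initial Administration of IP", and the others carry the same 45-day limit in their titles. The columns are Cohort 1, Cohort 2, Cohort 4 active, one placebo column in which "the two Placebo groups (Cohorts 3 and 4) will be pooled together", and a total.

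The windows are set by cohort. Cohorts 1-3 events count from the first dose until the date of Dose 2. Cohort 4 events count until the Day 45 visit; for a Cohort 4 subject who does not attend it, "all AEs will be included that occur up to and including 44 days" from the first dose. Nothing is said about a Cohorts 1-3 subject who has no Dose 2. The section's default is that events starting after a subject's "final scheduled study visit will not be included in table summaries".

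SAP Section 3.3 cites the "Cohorts 1-3 Randomization Plan, v1.0, 16May2022 and Cohort 4 Randomization Plan, v1.0, 18Apr2024". Protocol Section 3.1.3, in the version that adds Cohort 4, states: "All subjects in Cohorts 1-3 of the Phase 2 clinical study completed their last subject visit". SAP Table 1 lists the Cohort 4 placebo arm separately, as "Group 7 Placebo", alongside Group 5 for Cohort 3.

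**The concern.** The tables exist to compare rates, yet no active group has the pooled placebo column as its own randomized control. Cohorts 1-2 were randomized against Cohort 3 only, and Cohort 4 active against Cohort 4 placebo only, about two years apart by the dates of the randomization plans. If the background rate changed between the two periods, the pooled column moves the apparent drug effect in opposite directions for the repeat-dose and single-dose cohorts.

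Ascertainment before Day 45 also differs. Both sets of subjects have 24-hour, 72-hour, Day 8, Day 15 and Day 45 visits. Cohorts 1-3 also have 24-hour safety labs, a Day 15 ECG and a 1-hour stay; Cohort 4 has an 8-hour stay and a Day 30 visit (Protocol Sections 5.1, 8.4 and 9.2). The adverse-event definition in Protocol Section 9.8.1 includes abnormal laboratory findings, so the lab schedule can affect counts. Eligibility differs in one respect, the THC rule for Cohort 4 (Protocol Section 5.2, inclusion criterion 8).

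The window gap is separate. A subject without Dose 2 stays in the Safety population (at least one dose, SAP Section 7.1.2). SAP Section 9.9 plans to tabulate such subjects, and Protocol Section 6.2 asks for safety follow-up where possible. Read literally, that subject's events count to the final scheduled visit, about Day 240, under a title that says 45 days.

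**Working it through.** **Planned sizes.** Cohorts 1-3 are allocated equally over five groups: 5 x 75 = 375. Cohort 4 is 4:1: 250 x 4/5 = 200 active and 250 x 1/5 = 50 placebo. The total is 375 + 250 = 625, as in SAP Table 1. No power calculation bears on this point.

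**Separation in time.** 16 May 2022 to 18 Apr 2024 is 703 days, about 23 months. Protocol Section 5.1 lists all four cohorts as concurrent, but that cannot hold for Cohort 4 given Section 3.1.3.

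**Pooling.**
- Pooled n = 75 + 50 = 125, so the weights are 75/125 = 0.6 and 50/125 = 0.4.
- Let p3 and p4 be the background rates in the two enrolment periods and D = p3 - p4. Pooled placebo = 0.6 p3 + 0.4 p4.
- With no drug effect, Cohort 1 or 2 minus pooled placebo = p3 - (0.6 p3 + 0.4 p4) = +0.4D.
- With no drug effect, Cohort 4 active minus pooled placebo = p4 - (0.6 p3 + 0.4 p4) = -0.6D.

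D is not in the documents. Over an assumed range:

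| D (points) | Cohorts 1-2 minus pooled | Cohort 4 minus pooled |
|---|---|---|
| 0 | 0 | 0 |
| 5 | +2 | -3 |
| 10 | +4 | -6 |

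A negative D reverses both signs.

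**Window.** Assumptions: constant hazard, 44-day risk of 30%, and follow-up to Day 240 (239 days after the first dose).
- Chance that a subject without Dose 2 is counted: 1 - (1 - 0.30)^(239/44) = 0.856, against 0.30 with a 44-day cut-off. The excess is 0.556.
- Rise in the arm's percentage = 0.556 x the share without Dose 2: 1.7 points at 3%, 2.8 at 5%, 5.6 at 10%, and 0 if none.
- With a 44-day risk of 20% or 40%, a 5% share gives 2.5 or 2.7 points.

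This excess also enters the pooled placebo through Cohort 3. At 5% in each of Cohorts 1-3, pooled placebo = 0.6 x 32.8 + 0.4 x 30 = 31.7%. Cohort 4 active at 30% then looks 1.7 points better, and Cohorts 1-2 at 32.8% look 1.1 points worse, with no true difference.

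**The case against.** The strongest reply is that these tables are descriptive, no formal hypothesis testing is planned, and the pooled column is openly labelled. The main adverse-event tables are by treatment group and so keep the two placebo groups apart, and listings show every event. For Cohort 4, a single-dose cohort, the main table against its own placebo already includes the first 45 days. The reactogenicity table is split by dose for Cohorts 1-3 and is not pooled. Pooling also gains precision. All of this is true and limits the point to three tables. It does not remove the point: the main tables run to the final visit, and the reactogenicity table covers only listed reactions. Neither gives an overall or organ-class comparison restricted to the period before Dose 2.

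On the window, a programmer could infer a 45-day limit from the titles and the stated goal. That is probably the intent, but the text gives Cohort 4 an explicit fallback and Cohorts 1-3 none. The figures are an upper range, since some subjects who miss Dose 2 will leave follow-up. If the share is similar across Cohorts 1-3, the excess largely cancels when Cohorts 1-2 are read against Cohort 3 alone.

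The sign and size of D cannot be inferred, because the ascertainment differences point both ways. A direct reading of Cohort 2 against Cohort 4 also remains non-randomized however placebo is shown. Both limits stand.

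**Conclusion.** The point holds. The three tables state a comparative goal, use a placebo column that mixes two non-concurrent randomizations, and leave the Cohorts 1-3 window open for subjects without Dose 2. The pooling shift of +0.4D and -0.6D is exact for the planned sizes; D itself is unknown and could be zero. The window effect of about 1.7 to 5.6 points per arm rests on an assumed 30% 44-day risk, constant hazard, full follow-up to Day 240 and 3% to 10% of the arm missing Dose 2; it is zero if nobody does. No test or power is affected. The change should be made because these are the only planned overall and organ-class tables that put the single-dose and repeat-dose cohorts on the same period, and safety is a primary objective.

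**What to change.** In these three tables, show Cohort 3 placebo and Cohort 4 placebo in separate columns. Read Cohorts 1-2 against Cohort 3, and Cohort 4 active against Cohort 4 placebo. Keep the pooled column, if wanted, as a supplement labelled non-concurrent.

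Add one sentence to SAP Section 9.10.1: for a Cohorts 1-3 subject who does not receive Dose 2, adverse events are included up to and including 44 days after the first dose, as already planned for Cohort 4. Leave the rule for subjects who do receive Dose 2 unchanged, so that no event before Dose 2 is dropped.

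The cost is two extra columns in three tables and one sentence, with no new data. Each separate column is less precise. At an assumed 30% rate the 95% half-width, 1.96 x sqrt(0.3 x 0.7/n), is 8.0 points for n = 125, 10.4 for n = 75 and 12.7 for n = 50. For an assumed 2% event, the chance of at least one placebo case, 1 - 0.98^n, is 92%, 78% and 64% respectively. Keeping the pooled supplement offsets that loss.
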